4.2 Secondary Objectives

The secondary objectives are:

- 1) Among all subjects enrolled in the study, to describe time to kidney transplant and cumulative incidence of each type of transplant: a study-eligible HCV RNA-positive kidney (Arm 1), a study-eligible HCV RNA-negative/HCV antibody-positive kidney (Arm 2A), or a kidney transplant performed as part of standard of care treatment (Arm 2B).

2) To describe clinical outcomes while on the waitlist after consent (Serious Adverse events [SAEs], delisting from waitlist, death) between those who receive a study-eligible HCV RNA-positive kidney (Arm 1) and in subjects consented for this study who do not receive a study-eligible kidney transplant from an HCV RNA-positive donor (all Arm 2 subjects) overall and with breakdown by the 3 categories of Arm 2 as below:

A: subjects who receive a kidney from a study-eligible HCV RNA-negative/HCV Ab-positive donor

B: subjects who receive a standard of care kidney transplant

C: subjects who were not transplanted within 1 year of consent

Hereafter, these categories will be referred to as Arms 2A, 2B and 2C.

A “standard of care” transplant will be defined as any of the following kidney transplants: a deceased donor HCV RNA-positive kidney transplant that did not meet donor criteria for Arm 1 or HCV RNA-positive kidney transplant that place after last transplant allowed for Arm 1 but met criteria for Arm 1 inclusion (2B1); a deceased donor HCV RNA-negative/HCV Ab-positive kidney transplant that either did not meet donor criteria or took place > 6 months after the last Arm 1 transplant (2B2); a deceased donor HCV RNA-negative/HCV Ab-negative transplant at a MYTHIC clinical site (2B3); any living donor kidney transplant at a MYTHIC clinical site (2B4); or any kidney transplant at a different center than the 7 clinical sites (2B5).

In addition, to compare the total number of inpatient hospital days while on the waitlist and after study consent in those who did receive a study eligible HCV RNA-positive kidney (Arm 1) vs total inpatient hospital days in those who did not (Arm 2) overall and with breakdown by the 3 categories of Arm 2 (2A, 2B and 2C).

3) To describe clinical outcomes and data post-transplant (death, graft failure, acute allograft rejection, delayed graft function, estimated glomerular filtration rate [eGFR], proteinuria, ALT elevation > 5 times the upper limit of normal (ULN), SAEs)

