5.0 Investigational Plan

5.1 Overall Study Design, Rationale and Plan: Description

This is a Phase 4, open-label, multi-center, 2-arm study with the primary objective of evaluating the efficacy (SVR12) and safety of the fixed-dose combination tablets of glecaprevir/pibrentasvir (G/P) in HCV-negative subjects who receive a kidney transplant from an HCV RNA-positive deceased kidney donor. Among 90 subjects consented for trial participation, 30 subjects at up to 7 sites are planned to receive an HCV RNA-positive kidney and will be enrolled into a post-transplant treatment arm (Arm 1) receiving open-label G/P for 8 weeks post-transplant. The remaining consented patients who do not receive a study eligible kidney from an HCV RNA-positive donor will be followed in Arm 2 for the minimum duration of 1 year post-enrollment (Arm 2B and 2C), or 24 weeks post-transplant, whichever is longer (Arm 2A). These Arm 2 subjects include patients who do

not receive a kidney transplant (Arm 2C) or who receive a study eligible kidney from an HCV RNA-negative/HCV Ab-positive donor (Arm2A), or from a standard of care donor (Arm 2B). Follow-up for study participants who receive a kidney transplant at a non-study site (Arm 2B5) will be censored at transplantation.

For subjects of Arm 1 of the study, the first dose of G/P will be given as early as 3 days post-transplant. Patients must be out of the ICU, able to eat and drink, take oral medications, and G/P treatment can be safely initiated orally as judged by the site investigator.

Enrolled subjects will be activated in the United Network for Organ Sharing (UNOS) allocation system as eligible for kidney allograft offers from deceased donors that are HCV RNA-positive, HCV Ab-positive, or both.

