8.1.4 Secondary Clinical Outcomes

Secondary clinical outcome analyses will be performed for subjects prior to kidney transplant in both Arms 1 and 2, and post kidney transplant for those who receive a kidney transplant in Arms 1 and 2. For details on safety reporting and periods of safety reporting see section 6.1.4.

The cumulative incidence function curves of time to kidney transplant will be created for each type of kidney transplant (Arms 1, 2A, 2B), and cumulative incidence and standard error (SE) will be calculated for each type of kidney transplant.

An exploratory analysis will create cumulative incidence function curves of time to kidney transplant for the subgroups of Arm 2B if sufficient subjects are enrolled in Arm 2B.

The number and percentage of subjects with clinical outcomes while on waitlist and after study consent (SAEs, delisting from waitlist, death) among subjects who receive an HCV RNA-positive kidney (Arm 1) and among those subjects who do not receive an HCV RNA-positive kidney (all Arm 2 subjects) overall and with breakdown by category of Arm 2 (2A, 2B, 2C). In addition, the total number of inpatient hospital days while on waitlist in those who did receive an HCV RNA-positive kidney (Arm 1) and total inpatient hospital days in those who did not (Arm 2) overall and with breakdown by category of Arm 2 will be summarized descriptively with mean, median, standard deviation (SD), minimum and maximum.

We will match MYTHIC trial participants 1:3 to comparators derived from the Organ Procurement and Transplantation Network database. Matching will be based on demographics and baseline characteristics known to influence waiting time, including waiting list priority, blood group, geographic region, and sensitization. A comparison of time to kidney transplantation between the kidney transplant candidates enrolled in the MYTHIC trial and OPTN comparators will be performed using a Cox proportional hazards model.

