Summary of Statistical Analysis Plan for MYTHIC Study

[Draft: April 26, 2020]

Part	Patient Group(s)	Outcome	Statistical Analysis ^a
1	Arm 1 (ITT)	SVR12	- estimated probability of SVR12 and 95% confidence interval (CI) - exact binomial calculations
2	Arm 1 (ITT)	Virologic failure (VF)	- estimated probability of SVR12 and 95% confidence interval (CI) - exact binomial calculations
3	Arm 1 (ITT)	Post-treatment virologic relapse	- estimated probability of SVR12 and 95% confidence interval (CI) - exact binomial calculations
4	All patients	HCV-viremic kidney transplant (KT); i.e., Arm 1 KT	- cumulative incidence and 95% CI - death and other KT types treated as competing risk - estimate non-parametrically, using Lin (1997) which proceeds through the cause-specific hazards, or Fan (2013) which uses Inverse Probability of Censoring Weighting (IPCW).
5	All patients	Non-HCV-viremic KT; i.e., Arm 2A-2B KT	- same as for component (4).
6	All, by Arm	Hospital admissions	- Arm treated as a time-dependent treatment - crude hospitalization rate per 100 patient-years (PY) and 95% CI - use robust variance estimator, to account for correlation among hospital admissions within-patient
7	All, by Arm	Hospital admissions	- Arm treated as a time-dependent treatment - proportional rates model (Lin et al., 2000) - robust SEs, to account for clustering within-patient
8(a)	All, and SRTR* controls	Kidney transplant	- exclude, from SRTR, all patients who indicated consent to receive an HCV-viremic KT (hereafter: SRTR*) - estimate prognostic score using SRTR* patients: KT as event - 1:5 matching (MYTHIC : SRTR*) based on prognostic score with caliper - Cox regression, with MYTHIC as lone covariate, stratified by matched set

8(b)	All, and SRTR* controls	Kidney transplant	Same as 9(a), but using exact matching on small set of predictors, with prognostic score used to break ties among potential matches
9	Arm 1 – ITT	Compliance	Treated as repeated binary (0/1) data, with 1 indicating compliance (i.e., having taken 80-120% of prescribed pills)
10	Arm 1 – ITT	Death	Time to event; Cox regression
11	Arm 1 – ITT	Graft failure	Time to event; Cox regression
12	Arm 1	Delayed graft function	DGF: binary (0/1) response. Compute OBS/EXP, where OBS=observed number of DGFs for Arm 1 and EXP= expected count based on logistic regression model fitted to HCV-negative UNOS patients from large academic centers

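### SAP Parts 4 and 5 equate kidney HCV status with study arm, so an HCV RNA-positive 2B1 transplant would be reported as non-viremic; Part 5 also pools Arms 2A and 2B, and the eGFR comparison has no donor-quality check

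*SAP*

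**What the plan says.** **Transplant incidence.** SAP Part 4 estimates the cumulative incidence of "HCV-viremic kidney transplant (KT); i.e., Arm 1 KT", with death and other transplant types as competing risks. Part 5 does the same for "Non-HCV-viremic KT; i.e., Arm 2A-2B KT".

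Protocol section 4.2 splits Arm 2B by kidney source. Subgroup 2B1 is "a deceased donor HCV RNA-positive kidney transplant that did not meet donor criteria for Arm 1 or HCV RNA-positive kidney transplant" performed after the last one allowed for Arm 1 although it met the Arm 1 criteria. Subgroup 2B5 is "any kidney transplant at a different center than the 7 clinical sites (2B5"), with no donor HCV status stated. Section 8.1.4 says that cumulative incidence curves "will be created for each type of kidney transplant (Arms 1, 2A, 2B"), and adds exploratory curves "for the subgroups of Arm 2B if sufficient subjects are enrolled in Arm 2B".

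**Allograft function.** SAP Part 16 compares eGFR between Arm 1 and '2AB' in a linear mixed model and names no covariate. Protocol section 8.1.4 sets the eGFR comparator as 2A plus 2B1 to 2B4. Donors for Arms 1 and 2A must have KDPI of 0.85 or less (sections 5.2.2 and 5.2.2.2); standard of care kidneys have no study allograft criteria. KDPI is among the donor variables in section 8.1.1.

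**Proteinuria.** SAP Part 17 uses '2AB'. Section 8.1.4 compares Arm 1 with Arm 2A only. Objective 3 in section 4.2 covers 2A and 2B1 to 2B4, together and apart.

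**The concern.** The labels in Parts 4 and 5 treat study arm and donor viremia as the same thing, and the protocol's definitions show that they are not. A reader would take Part 4 as the incidence of all viremic transplants and Part 5 as the incidence of non-viremic transplants. Neither holds once a 2B1 transplant occurs. How readily candidates obtain each kidney type is the subject of secondary objective 1, so the label is part of the result.

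Pooling 2A with 2B also loses a distinction that the protocol makes. Arm 2A kidneys come from antibody-positive, RNA-negative donors who meet the study criteria; 2B holds everything else.

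The eGFR comparison is not randomised: arm follows from the kidney accepted. One group is partly free of the KDPI limit that binds the other. If donor quality differs, an eGFR difference could be read as an effect of the viremic kidney or its treatment, or could hide one.

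**Working it through.** **1. Is 2B1 inside the Part 5 event?** Part 5 takes all of 2A and 2B. 2B1 is a subgroup of 2B, and both limbs of its definition require an HCV RNA-positive donor. So a 2B1 transplant is a Part 5 event labelled non-viremic, and in Part 4 it falls under other transplant types, a competing risk.

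**2. Can a 2B1 transplant happen?** Enrolled subjects are activated as "eligible for kidney allograft offers from deceased donors that are HCV RNA-positive" (among others). After the 30th Arm 1 transplant, those remaining may still accept a standard of care kidney (section 5.1.5), which includes 2B1. They "will be followed in Arm 2 for the minimum duration of 1 year post-enrollment". Section 8.2 expects at least 40 of 90 transplanted in about 6 months (40/90 = 44%, as stated there), which leaves up to 90 − 40 = 50 still waiting.

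**3. Size.** The plan gives no figure for 2B1, so the number of cases k is an assumption. Each case is 1/90 = 1.1 percentage points (1/75 = 1.3 at the lower enrolment estimate). Taking 30 Arm 1 transplants and 40 − 30 = 10 others, as crude proportions of 90 with censoring ignored:

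| k | Viremic, SAP label | Viremic, by donor RNA | Non-viremic, SAP label | Non-viremic, by donor RNA (Wilson 95% CI) |
|---|---|---|---|---|
| 0 | 30/90 = 33.3% | 33.3% | 10/90 = 11.1% | 11.1% (6.1 to 19.3) |
| 1 | 33.3% | 31/90 = 34.4% | 11.1% | 9/90 = 10.0% (5.4 to 17.9) |
| 3 | 33.3% | 33/90 = 36.7% | 11.1% | 7/90 = 7.8% (3.8 to 15.2) |

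With 20 others (assumed, longer follow-up), the non-viremic figure is 22.2% as labelled, 21.1% for k = 1 and 18.9% for k = 3. One case is small against the interval.

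**4. Donor criteria in the eGFR comparison.** Arm 1 and Arm 2A: KDPI at most 0.85. Second limb of 2B1: met the Arm 1 criteria. Rest of 2B: no limit. The design therefore allows a difference in donor quality but does not create one. The documents give no effect of KDPI on eGFR, so no size is claimed.

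**5. Precision of a KDPI-adjusted deceased-donor analysis.** Living-donor recipients (2B4) have no KDPI and drop out. Take 30 in Arm 1 and n controls.

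- Leaving out m of n controls multiplies the standard error by √(1/30 + 1/(n−m)) / √(1/30 + 1/n). For n = 10: 1.041 (m = 1) and 1.150 (m = 3). For n = 20: 1.016 and 1.052.
- A KDPI imbalance of d SD (assumed) multiplies it by √(1 + d²pq), where p and q are the group shares. For n = 10, pq = 0.75 × 0.25 = 0.1875: 1.023 (d = 0.5) and 1.090 (d = 1). For n = 20, pq = 0.24: 1.030 and 1.114.
- Both together, n = 10 and m = 3, so pq = (30/37)(7/37) = 0.153: 1.150 × 1.019 = 1.17 (d = 0.5) and 1.150 × 1.074 = 1.23 (d = 1).

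These figures ignore any gain from variance that KDPI explains.

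**6. Proteinuria.** Table 6 schedules a urine protein/creatinine ratio for Arm 2A. For standard of care recipients, section 5.1.10 takes proteinuria from the medical record only where it exists. That is a plausible reason for the narrower comparison in section 8.1.4. Objective 3 is worded as description, section 8.1.4 as comparison.

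**The case against.** The strongest reply is that Parts 4 and 5 name the arms, so the events can be programmed without ambiguity and no subject changes arm. That stands: the error lies in what the estimate is called, and it is numerically nil if no 2B1 or viremic 2B5 transplant occurs.

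Four stronger readings are tempting, and the documents do not support them.

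- A reader might infer that '2AB' leaves the eGFR comparator open. It does not: section 8.1.4 gives 2A plus 2B1 to 2B4, and section 5.1 collects nothing on 2B5 after transplant. Including 2B1 there is the protocol's stated choice.
- A reader might infer that the protocol's restricted analyses (eGFR in recipients without HCV infection, and censoring at non-study-eligible HCV-positive transplants) have been withdrawn. The SAP calls itself a summary and a draft, and omission from it withdraws nothing. These analyses remain prespecified, so a further analysis excluding 2B1 is not needed.
- A reader might infer that donor quality differs by design. The design only permits it, and Arm 2A, with the same KDPI cap, may supply up to 20 comparators.
- A reader might carry 2A plus 2B1 to 2B4 over to Parts 17 and 18. For proteinuria, section 8.1.4 names 2A only; for BK virus the protocol has no comparison at all. The protocol's covariate list and Synopsis endpoint 3 concern the logistic regression of clinical outcomes, not eGFR.

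**Conclusion.** The kidney-type labels in Parts 4 and 5 contradict the protocol's definition of 2B1 and leave 2B5 unclassified, and Part 5 pools two arms that the protocol reports separately. The label error moves about 1.1 percentage points per 2B1 case on 90 enrolled. The number of cases is unknown, and the illustrations rest on assumed counts and crude proportions.

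The missing donor-quality adjustment in Part 16 is a gap in both documents and supports a supportive analysis, not a change to the main one. The proteinuria comparator needs reconciling. Overall severity: minor.

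**What to change.** - **Part 4:** label it as study-eligible HCV-viremic transplantation (Arm 1).
- **Part 5:** report Arm 2A and Arm 2B cumulative incidence separately. If a non-viremic incidence is also wanted, define it as 2A plus 2B2 to 2B4, show 2B1 as a viremic category, and class 2B5 by donor status where known and as unknown otherwise. The definition of 2B4 does not state donor HCV status either, so confirm it from the donor record.
- **Part 16:** state that '2AB' means 2A plus 2B1 to 2B4. Beside the main model, add a supportive analysis in deceased-donor recipients adjusted for KDPI.
- **Part 17:** say in one sentence how '2AB' fits with section 8.1.4 and objective 3, given that standard of care proteinuria is not scheduled.

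The cost is SAP wording and one extra model. KDPI and the 2B subgroups are already to be summarised (section 8.1.1), and the main eGFR comparator is unchanged. The loss of precision falls on the supportive analysis only. With 10 controls, the standard error rises by about 2% to 9% from KDPI imbalance, or 4% to 15% from leaving out one to three living-donor recipients. With three left out and imbalance as well, the rise is about 17% to 23%. Living-donor cases should be few, since candidates with an available compatible living donor are not enrolled (section 5.2.1.1).

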The primary efficacy endpoint is sustained virologic response 12 weeks post dosing (SVR₁₂), defined as HCV RNA < LLOQ 12 weeks after the last actual dose of G/P. The SVR₁₂ rate will be determined from all enrolled subjects who received an HCV RNA-positive kidney in Arm 1 and received at least one dose of G/P study drug along with a two-sided 95% confidence interval. The confidence interval for the SVR₁₂ rate will be calculated using Wilson's score method.

The secondary efficacy endpoints for recipients of kidney transplants from HCV RNA-positive donors in Arm 1 are:

1. The percentage of subjects with on-treatment virologic failure;
2. The percentage of subjects with post-treatment virologic relapse.

Additional efficacy analyses will be performed.

Clinical endpoints:

Secondary endpoints for the secondary objectives are:

1. Among all subjects enrolled in the study who receive a kidney transplant, the time to kidney transplant and cumulative incidence of each type of transplant will be determined for: study-eligible HCV RNA-positive kidneys (Arm 1), study-eligible HCV RNA-negative/HCV Ab-positive kidneys (Arm 2A), and standard of care kidney transplants (Arm 2B).
2. The number and percentage of subjects with clinical outcomes while on the

waitlist (SAEs, delisting from waitlist, death) among subjects who receive an HCV RNA-positive kidney in Arm 1 and among those subjects who do not receive a study eligible HCV RNA-positive kidney (all Arm 2 subjects) overall and with breakdown by the category in Arm 2 (2A, 2B and 2C). In addition, the total number of inpatient hospital days while on waitlist in those who did receive a study eligible HCV RNA-positive kidney (Arm 1) and total inpatient hospital days in those who did not (Arm 2) overall and with breakdown by categories of Arm 2 will be summarized descriptively.

3. The number and percentage of subjects with the following clinical outcomes and data post-transplant as applicable: death, graft failure, acute allograft rejection, delayed graft function, ALT elevations > 5x ULN, and SAEs. The difference in the overall percentage of subjects with clinical outcomes and data post-transplant between Arm 1 and Arms (2A + 2B1 – 2B4) will be assessed by logistic regression with Arm as a factor and appropriate covariates to adjust for possible differences between Arms including waiting list priority, blood group, geographic region and sensitization as appropriate.

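### SAP Part 5 has one row for Arm 2A and Arm 2B transplants together, so no listed analysis gives the cumulative incidence of either type alone as the protocol requires, and the row's label does not match its arms

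*SAP*

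**What the plan says.** **Protocol.** Secondary objective 1 (Synopsis and section 4.2) is to describe, among all enrolled subjects, time to transplant and the cumulative incidence of each transplant type. After Arm 1 it lists "a study-eligible HCV RNA-negative/HCV antibody-positive kidney (Arm 2A), or a kidney transplant performed as part of standard of care treatment (Arm 2B"). Secondary endpoint 1 in the Synopsis names the same three types. Section 8.1.4 gives the analysis: "The cumulative incidence function curves of time to kidney transplant will be created for each type of kidney transplant (Arms 1, 2A, 2B"). It adds that "cumulative incidence and standard error (SE) will be calculated for each type of kidney transplant", and plans exploratory curves for the subgroups of Arm 2B if enough subjects fall there.

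**SAP (draft summary dated April 26, 2020).** Two rows concern cumulative incidence of transplant, both in all patients:
- Part 4 has the event "HCV-viremic kidney transplant (KT); i.e., Arm 1 KT", with "death and other KT types treated as competing risk", estimated non-parametrically.
- Part 5 has the event "Non-HCV-viremic KT; i.e., Arm 2A-2B KT", analysed as in Part 4.

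The SAP gives no reason for listing two events where the protocol lists three.

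**The concern.** The two types that share a row differ in definition and in availability. An Arm 2A transplant uses an RNA-negative, antibody-positive kidney that meets the study's donor criteria. Arm 2A is limited to 20 subjects and closes 24 weeks after the 30th Arm 1 transplant (section 5.1). Arm 2B is everything else, from 2B1 to 2B5 (section 4.2): RNA-positive kidneys outside Arm 1, antibody-positive kidneys outside Arm 2A, antibody-negative deceased-donor kidneys, living-donor kidneys, and any transplant at another centre. A pooled curve does not show which of these produced the events.

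At stake is a named secondary endpoint. If the SAP is carried out as listed, the protocol's description by transplant type would be delivered for Arm 1 only. The label adds a second problem: a programmer given Part 5 cannot tell whether a 2B1 transplant is an event or a competing event.

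**Working it through.** **Step 1: look for 2A or 2B alone in the SAP.**

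| SAP part | Content | Incidence of 2A or 2B alone? |
|---|---|---|
| 1–3 | Virologic outcomes, Arm 1 | No |
| 4 | Arm 1 transplant | No |
| 5 | 2A and 2B in one row | No, if pooled |
| 6, 7, 15 | Hospital admissions and SAEs by arm | No |
| 8(a), 8(b) | Any kidney transplant against registry controls | No |
| 9–14 | Compliance and clinical outcomes, Arm 1 | No |
| 16–18 | eGFR, proteinuria, BK virus, Arm 1 and 2AB | No |

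**Step 2: can the pooled curve be separated?** With cause-specific hazards, the cumulative incidence of type k is F_k(t) = ∫ S(u−) dΛ_k(u), where S is the probability of having had no event of any kind. Hence F_pooled(t) = F_2A(t) + F_2B(t). The separate curves determine the pooled curve, but the pooled curve does not determine its two components.

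**Step 3: illustration.** The plan has no figure here to reproduce. Inputs:
- At least 40 of 90 transplanted (section 8.2): 40/90 = 44.4%.
- Target of 30 Arm 1 transplants (Synopsis).
- Assumption, not in the documents: the total is exactly 40 and all 30 Arm 1 transplants are among them. Section 8.2 refers to about 6 months of follow-up, whereas 30 is the whole-trial target.

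This leaves 40 − 30 = 10 pooled events. The crude incidence, ignoring censoring, is 10/90 = 11.1%, with SE = √(0.111 × 0.889 / 90) = 3.3 percentage points. The same pooled result fits every row below (Wilson 95% intervals):

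| 2A events | 2A incidence | 2B events | 2B incidence | Part 5 reports |
|---|---|---|---|---|
| 0 | 0% (0% to 4.1%) | 10 | 11.1% (6.1% to 19.3%) | 11.1% |
| 5 | 5.6% (2.4% to 12.4%) | 5 | 5.6% (2.4% to 12.4%) | 11.1% |
| 10 | 11.1% (6.1% to 19.3%) | 0 | 0% (0% to 4.1%) | 11.1% |

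A second, separate assumption: 2A reaches its limit of 20 and 2B has 10, so that 30 + 20 + 10 = 60 subjects are transplanted. Part 5 would then report 30/90 = 33.3%, where the protocol asks for 20/90 = 22.2% and 10/90 = 11.1%.

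**Step 4: the label.** Section 4.2 defines 2B1 as deceased-donor RNA-positive kidneys that fail the Arm 1 donor criteria, or RNA-positive kidneys transplanted after the last one allowed in Arm 1. Read by donor viremia, a 2B1 transplant is outside Part 5. Read by arm, it is inside. Part 4 has the mirror image: 2B1 is viremic but is not Arm 1.

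**Step 5: the denominator.** Objective 1 and SAP Parts 4 and 5 use all enrolled subjects, whereas the Synopsis endpoint is worded for subjects who receive a transplant. In the first illustration this is 10/90 = 11.1% against 10/40 = 25.0%, so the rewritten rows should state which applies.

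**The case against.** **The SAP is a draft summary.** It does not say that it replaces section 8.1.4, which still calls for three curves. This stands. The supportable claim is that no listed SAP part gives 2A or 2B alone. A reader might infer that these incidences will never be estimated, and the documents do not show that.

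**Pooling is inferred, not stated.** Parts 16–18 write the combined group as 2AB, whereas Part 5 writes 2A-2B. The competing-risk rule carried over from Part 4 speaks of other types in the plural, although only Arm 1 would remain if 2A and 2B were one event. This is a fair point, but one row with one named outcome, set against Arm 1, is most naturally read as one event. If two curves are intended, the row still has to say so.

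**The analysis is descriptive.** There is no hypothesis test, 2A is limited to 20 subjects, and neither the primary endpoint nor data collection changes. This is correct and limits the weight of the point.

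**A stronger reading is tempting.** A reader might infer that the split is needed to learn how much antibody-positive kidneys add to access, with 2B standing for transplants that would have happened without the study. The documents do not support this. Objective 1 only describes, and the planned access comparison is with external registry candidates. Arm 2B is also not a clean background group: it contains 2B1 and 2B2, and enrolled subjects are activated for HCV-positive offers (section 5.1), so some 2B transplants may themselves follow from enrolment.

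**Conclusion.** The point holds as a mismatch between protocol and SAP on a named secondary endpoint. The protocol asks for three incidences and the SAP lists two. The part left out cannot be recovered from the reported curve, and the label on the combined row is inconsistent because of 2B1. The conclusion rests on reading Part 5 as a single event and on the listed SAP parts being complete. It rests on no event count. The 0% to 11.1% range for 2A shows only what a sum hides, under an assumed 10 pooled events among 90. The correction should be made before analysis. It restores a description by transplant type and says nothing about what would have happened without the study.

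**What to change.** Replace Part 5 with two rows, using the Part 4 estimator among all enrolled subjects:
- **5a:** Arm 2A transplant as the event; death, Arm 1 and Arm 2B transplants competing.
- **5b:** Arm 2B transplant, including 2B1, as the event; death, Arm 1 and Arm 2A transplants competing.

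Report the cumulative incidence with its SE for each, as section 8.1.4 requires, alongside the SAP's 95% confidence interval. Drop the non-viremic label and define events by arm, in Part 4 as well, so that each transplant falls in exactly one row. Keep a pooled 2A and 2B curve only as a supplement. Its point estimate is the sum of 5a and 5b, but its SE must allow for their covariance.

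The cost is one additional SAP row and some rewording, with no new data and no new method.
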